4.1 Populations

Per Protocol (PP)

All included study subjects completing the whole study period (complete cases) will be seen as the primary population for the analysis. For a specific analysis, study subjects with missing data on any of the variables in the model will be excluded from the analysis.

5. Analyses

All outcomes will be presented using descriptive statistics; normally distributed data by the mean and standard deviation (SD) and skewed distributions by the median and interquartile range (IQR). Binary and categorical variables will be presented using counts and percentages. SPSS statistical software version 24 (SPSS Inc., Chicago, Ill., USA) will be used for all statistical analysis.

5.1 Primary outcome

The primary analysis will compare fasting plasma copeptin concentration between baseline and 6 weeks using a paired T-test or Wilcoxon's paired rank test depending on distribution.

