Population: We previously showed that subjects with high VP (i.e. copeptin of >6.1 pmol/L in women and >10.7 pmol/L in men), which corresponds to 25% of the population aged 20-75y, has 3-4 times elevated risk for diabetes development, i.e. a magnitude of risk that is similar to that of obesity, and a doubled risk of CVD mortality. In addition, the high VP target group of this study has a urine osmolality of >600 mosm/kg water, i.e. concentrated urine concordant with a low water intake.

[figure not shown]
Screening and inclusion process: Study subjects (n=30) will be recruited from the Malmö Offspring Study (n=1547) (<http://www.med.lu.se/mos>). Copeptin will be measured in -80 degree frozen plasma samples from this study. Assuming that the prevalence of having high plasma copeptin concentration of >6.1 pmol/L in women and >10.7 pmol/L in men will be approximately 25%, around 400 individuals will have high copeptin concentrations and will be eligible for the current study. These individuals will be contacted by letter and subsequently by telephone. Individuals interested in participation, who do not have any medication or disease implying immediate exclusion (see inclusion and exclusion criteria below), will be invited to participate in the current study.

Inclusion criteria will be provision of informed consent, age 20-75 years with high plasma concentration of VP (plasma concentration of copeptin of >6.1 pmol/L in women and >10.7 pmol/L in men) and 24-hour urine osmolality ≥ 600 mosm/kg water.

Exclusion criteria will be 24-hour urine volume >1.5 L, pregnancy or breastfeeding, plasma sodium <135 mM, use of diuretics, lithium or SSRI drugs, chronic kidney disease (eGFR <30 mL/min), heart failure, inflammatory bowel disease, type 1 diabetes or type 2

diabetes treated with insulin and vulnerable subjects (subjects with legal guardian, with loss of personal liberty).

Figure 1. Study protocol

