Intervention: All participants will be instructed to add 1.5 L of plain water daily on the top of habitual intake (intervention) during six weeks (Figure 1). At baseline, all participants also will receive general oral and written advice on diet and physical activity. Adherence to high water intake will be achieved by coaching at the clinic visit and by regular telephone contacts with the participants. We benefit from shared experience of how to successfully perform the water intervention by collaboration with [name], London Health Science Centre, Canada (co-investigator in current project) who is PI of the Chronic Kidney Disease Water Intervention Trial (WIT) (same water vs control intervention as in current study but primary outcome = effect of water on decline of GFR) whose Data Safety Monitoring Report was completed June 2015 and showed excellent separation in water intake during follow-up (measured by 24-hour urine volume) and safety. In accordance with the protocol of the WIT, adherence to high water intake will be achieved by coaching at the clinic visits and by regular telephone contacts. Furthermore, we will provide urine color charts to use at home to facilitate adherence to target urine concentration.

Outcome: We will test if six weeks of water supplementation of 1.5L extra water per day in low-drinkers with high copeptin significantly alter hydration markers in general and reduce plasma copeptin in particular. Furthermore, as fasting plasma glucose will be the primary endpoint of the long term RCT, we will also investigate whether the 6-week water intervention could significantly reduce fasting plasma glucose concentration. Significance of differences between baseline and after intervention will be tested using paired t-test or Wilcoxon's paired rank test depending on distribution. SPSS statistical software version 24 (SPSS Inc., Chicago, Ill., USA) will be used for all analyses. A 2-sided p value of <0.05 will be considered statistically significant.

Table 1. Schedule of visits and measures

				Follow-up ^b
--	--	--	--	-------------------------------

	Visit 1 ^{a,c}	Visit 2 (Inclusion) ^{a,c}	Baseline (Week 0)	3 weeks	6 weeks
Informed Consent Process and Informed Consent Form Signature	+				
Exclusion criteria check-up including pregnancy	+				
SURVEY					
Demographics			+		
Diet (4-day report)			+		+
Health history			+		+
Health-related quality of life			+		+
Hydration coaching ^c			+	+	+
CLINICAL					
Height (cm)			+		+

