The aim of this study is to perform a pilot study in 30 subjects, before the start of a long term RCT. Thus, we have not performed a power calculation. In the study we will test for the first time if six weeks of moderate water supplementation (1.5L extra water per day) in low-drinkers with high plasma levels of copeptin can significantly reduce plasma copeptin concentration. The primary outcome measure of the study is the change of fasting plasma copeptin between baseline and 6 weeks of water intervention. Furthermore, the study is designed to investigate study logistics, safety, compliance and drop-out rate before the start of a long term (1 year) RCT. Finally, as fasting plasma glucose will be the primary endpoint of the long term RCT, we also aim at investigating whether the 6-week water intervention can significantly reduce fasting plasma glucose concentration.

2. Sample size

A pilot study with 30 participants.

3. Outcomes

This section will present the outcomes investigated to answer the study aims and objectives. The analyses are described in section 5 Analyses.

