3.2 Secondary outcomes

24 hour urine osmolality (measured at baseline, at 3 weeks and at 6 weeks).

24 hour urine volume (measured at baseline, at 3 weeks and at 6 weeks).

Drinking water (measured at baseline and at 6 weeks).

Total water (measured at baseline and at 6 weeks).

Fasting plasma glucose concentration (measured at baseline, at 3 weeks and at 6 weeks).

Surveys

Health-related quality of life, fluid/water and dietary intake (using Riksmaten 2010), stool form (Bristol Stool Scale).

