5.2 Secondary outcomes

The secondary analyses will compare 24 hour urine osmolality, 24 hour urine volume, drinking water, total water and fasting plasma glucose concentration between baseline and 6 weeks using a paired T-test or Wilcoxon's paired rank test depending on distribution.

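### Do SAP 5.1 and 5.2 need to name the distribution that picks the test and promise a change estimate with a 95% CI?

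*Combined protocol and SAP*

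**What the plan says.** SAP 5.1 sets the primary test: "The primary analysis will compare fasting plasma copeptin concentration between baseline and 6 weeks using a paired T-test or" Wilcoxon's paired rank test, with the distribution deciding. SAP 5.2 uses the same rule for urine osmolality, urine volume, drinking water, "total water and fasting plasma glucose concentration between baseline and 6 weeks using a paired T-test or" the rank test. The protocol's Outcome paragraph describes the tests as tests of differences from baseline and adds: "A 2-sided p value of <0.05 will be considered statistically significant".

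The only reporting rule is in SAP section 5 and covers all outcomes: "normally distributed data by the mean and standard deviation (SD) and skewed distributions by the median and interquartile range (IQR"). SAP section 1 defines the primary outcome measure as the change in fasting copeptin from baseline to 6 weeks. Glucose is listed in SAP 3.2 by visit only: "Fasting plasma glucose concentration (measured at baseline, at 3 weeks and at 6 weeks"). SAP 4.1 analyses completers. On sample size, section 1 says: "Thus, we have not performed a power calculation". No confidence interval is mentioned anywhere.

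**The concern.** Two things look wrong. First, the word distribution has no object. It could mean the values at each visit or the within-person differences, and these can point to different tests. Second, the promised outputs may not show the size of the effect. If glucose is skewed, a literal reading gives two visit medians with IQRs and a p-value, with no estimate of the paired change.

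The entry criteria make skewness plausible. Copeptin is selected above sex-specific cut-offs: "age 20-75 years with high plasma concentration of VP (plasma concentration of copeptin of >6.1 pmol/L in women and >10.7 pmol/L in men"). For diabetes, the exclusions cover type 1 and type 2 "diabetes treated with insulin and vulnerable subjects", so other type 2 diabetes may enter and stretch the upper tail of glucose.

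The stake would be interpretation. Fasting glucose is to be the primary endpoint of the one-year RCT. With 30 people, no power calculation and no interval, a non-significant glucose result could mean no effect or too few participants.

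**Working it through.** The plan gives no sample-size or precision figure to reproduce. It also gives no SD or effect size, so every simulation input below is an assumption.

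**1. Which distribution the text points to.** The paired t statistic is the mean difference divided by (SD of the differences / √n). The Wilcoxon paired test ranks the differences. The Outcome paragraph speaks of differences, and SAP section 1 makes change the copeptin outcome. The ordinary reading is the distribution of the differences.

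**2. Whether the other reading would matter.** Both readings were compared with Shapiro-Wilk at 0.05 and n = 30.
- Lognormal values (log-SD 0.3-0.5, correlation 0.7-0.9, log-shift 0 to -0.3; 4,000 runs per scenario): the readings picked different tests in 47-54% of runs, but the verdict differed in only 0.7-4.2%.
- Copeptin selected at the two cut-offs, and glucose with mean 5.5, SD 0.5, a fall of 0.15 mmol/L, and 0-3 of 30 people with type 2 diabetes not treated with insulin (mean 8.0, SD 1.3); 2,000 trials per cell: the verdict differed in 0.2-5.1% and power by at most 1.5 points. Type I error, from the copeptin cells with no fall, was 0.041-0.055.

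**3. What can be recovered on the t-test branch.** In complete cases the mean change equals the difference of the two visit means. With an exact p-value, SD of change = |difference of means| × √n / t. In an illustrative data set (n = 30, p = 0.037) the true SD was 0.2738 and the recovered SD 0.2738. The interval follows from it.

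**4. What can be recovered on the Wilcoxon branch.** Visit medians and IQRs were held fixed at 5.58 (5.01-5.87) and 5.34 (4.80-5.72), and only the pairing was altered.

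| Pairing | Median change | SD of change | Wilcoxon p |
|---|---|---|---|
| aligned | -0.171 | 0.136 | <0.001 |
| shuffled | -0.210 | 0.853 | 0.24 |
| reversed | -0.237 | 1.357 | 0.52 |

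Visit summaries alone therefore do not determine the paired change. For copeptin this does not arise: SAP sections 1 and 5 together already allow a median (IQR) of the change. In simulation its SE was 0.79-0.98 times that of the mean change.

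**5. How often glucose reaches that branch.** Judged on the differences, normality fails in 5-6% of trials with no diabetic participant and in 18-32% with 1-3 of 30. In trials with 1-3 diabetic participants whose differences fail, the difference of visit medians has an SE about 1.16-1.50 times that of the mean paired change. That is like using 30/1.16² = 22 down to 30/1.50² = 13 of the 30 people. Taken over all such trials, whichever test applies, the ratio is 1.32-1.83, but this includes many trials where the t-test would be used.

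**6. What an interval would show.** Half-width = t(0.975, n-1)/√n × SD of change.
- n = 30: 2.045/5.477 = 0.373 SD.
- n = 24 (assumed 20% dropout): 2.069/4.899 = 0.422 SD.

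A just non-significant result at n = 30 has an interval reaching a fall of about 0.373 + 0.373 = 0.746 SD. If the SD of change is 0.3-0.6 mmol/L (assumed), that is 0.22-0.45 mmol/L.

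**The case for a change.** The strongest case for a change is about glucose. It is the variable the later trial rests on, and a before-after design in 30 people draws its strength from the pairing. On the median branch, the literal outputs discard the pairing, as step 4 shows. Two added sentences would cost nothing in data or visits.

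Part of this stands. The plan does not promise an interval, and an estimate with its interval is better reporting than a p-value alone. Three points weaken it as a reason to amend.

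- Silence in the SAP does not forbid reporting a change. Glucose is measured at baseline and 6 weeks in the same completers, so the change, its SD and its interval remain available.
- The branch at issue is uncommon for glucose unless diabetic participants enrol. The criteria permit that, but the documents do not say that it will happen.
- The natural remedy is mismatched. It would put a t-interval for the mean beside a Wilcoxon p-value exactly where the differences are skewed. In glucose trials with 1-3 diabetic participants whose differences fail normality, the two disagree in about 15-18%. That rate is conditional on such trials, so it is not on the same base as the 0.2-5.1% in step 2. It does show that the remedy brings contradictions of its own, although the t-interval still covers the true mean change in 94-98% of trials with non-normal differences.

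An estimate matched to the test, such as Hodges-Lehmann with the Wilcoxon test, avoids the conflict. An analyst can report it without any amendment.

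**Conclusion.** No change follows. This is missing detail that analysts fill sensibly. The ordinary reading of the test rule is the distribution of the paired differences, and the alternative reading changes the verdict in at most about 5% of simulated trials without harming type I error. For copeptin only the confidence interval goes unpromised. For glucose the change estimate, its SD and its interval go unpromised, but all can be computed from data the plan collects. No stated rule leads to a wrong result, and estimating an SD for the later RCT is not a stated aim of the pilot.

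The simulated rates rest on assumed distributions, correlations and numbers of diabetic participants. The half-widths (0.373 SD at n = 30, 0.422 SD at n = 24) need only n and the t distribution. The conclusion also assumes that the analyst reports the paired change for glucose and not two visit medians alone.

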5.2 Secondary outcomes

The secondary analyses will compare 24 hour urine osmolality, 24 hour urine volume, drinking water, total water and fasting plasma glucose concentration between baseline and 6 weeks using a paired T-test or Wilcoxon's paired rank test depending on distribution.
